9.1.2. Visit Windows

Visit windows will be allowed as indicated in [Table 12](#), [Table 13](#), [Table 14](#), and [Table 15](#).

The timings of the post-vaccination visits will be determined relative to the actual day of the corresponding vaccination. If a participant misses a vaccination, the post-vaccination visits will be calculated from the imputative vaccination date according to protocol.

Table 12: Visit Windows: Initial Safety Cohort (Cohort 1)

VISIT	Visit Day	Window	Primary Purpose
Visit 2	Day 1	--	FIRST STUDY VACCINATION
Visit 3	Day 8	±2 days	7-day post-first study vaccination safety only visit
Visit 4	Day 15	±2 days	14-day post-first study vaccination safety and immunogenicity visit
Visit 5	Day 29	±3 days	28-day post-first study vaccination safety and immunogenicity visit
Visit 6	Day 57	±3 days	SECOND STUDY VACCINATION
Visit 7	Day 64 (Vac 2 +7 days)	±2 days	7-day post-second study vaccination safety only visit
Visit 8	Day 85 (Vac 2 +28 days)	-3 days/+10 days	28-day post-second study vaccination safety and immunogenicity visit
Visit 9	Day 183 (Vac 1 +26 weeks)	±14 days	26-week post-first study vaccination safety and immunogenicity visit
Visit 10	Day 365	±2 months	THIRD STUDY VACCINATION (MONTH 12 BOOSTER)
Visit 11	Day 372 (Vac 3 +7 days)	±2 days	7-day post-third study vaccination safety only visit
Visit 12	Day 393 (Vac 3 +28 days)	±3 days	28-day post-third study vaccination safety and immunogenicity visit
Visit 13	Day 547 (Vac 3 +26 weeks)	±14 days	26-week post-third study vaccination safety and immunogenicity visit
Visit 14	Day 730 (Vac 3 +12 months)	±1 month	FINAL VISIT: 12-month post-third study vaccination safety and immunogenicity visit

Table 13: Visit Windows: Regimen Selection Cohort (Cohort 2)

VISIT	Visit Day	Window	Primary Purpose
Visit 2	Day 1	--	FIRST STUDY VACCINATION
Visit 3	Day 8	±2 days	7-day post-first study vaccination safety only visit
Visit 4	Day 15	±2 days	14-day post-first study vaccination safety and immunogenicity visit
Visit 5	Day 29	±3 days	28-day post-first study vaccination safety and immunogenicity visit
Visit 6	Day 57	±3 days	SECOND STUDY VACCINATION
Visit 7	Day 64 (Vac 2 +7 days)	±2 days	7-day post-second study vaccination safety only visit
Visit 8	Day 85 (Vac 2 +28 days)	-3 days/+10 days	28-day post-second study vaccination safety and immunogenicity visit
Visit 9	Day 183 (Vac 1 +26 weeks)	±14 days	26-week post-first study vaccination safety and immunogenicity visit
Visit 10	Day 365 (Vac 1 +12 months)	±1 month	12-month post-first study vaccination safety and immunogenicity visit
Visit 11	Day 547 (Vac 1 +18 months)	±1 month	18-month post-first study vaccination safety and immunogenicity visit
Visit 12	Day 730 (Vac 1 +24 months)	±1 month	FINAL VISIT for Groups 11-13 and Groups 16-18: 24-month post-first study vaccination safety and immunogenicity visit
Visit 13*	Day 912 (Vac 1 + 911 days)	±30 days	30-month post-first study vaccination immunogenicity visit
Visit 14*	Day 1095 (Vac 1 +1094 days)	±30 days	FINAL VISIT: 36-month post-first study vaccination immunogenicity visit

*Visits during long-term follow-up phase for participants in Groups 14 and 15 only.

Table 14: Visit Windows: Expanded Safety Cohort (Cohort 3) - One-dose Regimen and Month 12 and Month 24 Booster

VISIT	Visit Day	Window	Primary Purpose
Visit 1	Day 1	–	FIRST STUDY VACCINATION
Visit 2	Day 8	±2 days	7-day post-first study vaccination safety only visit
Visit 3	Day 15	±2 days	14-day post-first study vaccination safety and immunogenicity visit
Visit 4	Day 29	±3 days	28-day post-first study vaccination safety and immunogenicity visit
Visit 5	Day 57	±3 days	56-day post-first study vaccination safety and immunogenicity visit
Visit 6	Day 85 (Vac 1 +12 weeks)	-3/+10 days	12-week post-first study vaccination safety and immunogenicity visit
Visit 7	Day 183 (Vac 1 +26 weeks)	±14 days	26-week post-first study vaccination safety and immunogenicity visit
Visit 8	Day 365	–2 months	SECOND STUDY VACCINATION (MONTH 12 BOOSTER)
Visit 9	Day 372 (Vac 2 +7 days)	±2 days	7-day post-second study vaccination safety only visit
Visit 10	Day 393 (Vac 2 +28 days)	±3 days	28-day post-second study vaccination safety and immunogenicity visit
Visit 11	Day 547 (Vac 2 +26 weeks)	±14 days	26-week post-second study vaccination safety and immunogenicity visit
Visit 12	Day 730 (Vac 1 +729 days)	±30 days	THIRD STUDY VACCINATION (MONTH 24 BOOSTER)
Visit 13	Day 737 (Vac 3 +7 days)	±2 days	7-day post-third study vaccination safety only visit
Visit 14	Day 744 (Vac 3 +14 days)	±2 days	14-day post-third study vaccination safety and immunogenicity visit
Visit 15	Day 758 (Vac 3 +28 days)	±3 days	28-day post-third study vaccination safety and immunogenicity visit
Visit 16	Day 912 (Vac 3 +182 days)	±14 days	26-week post-third study vaccination safety and immunogenicity visit
Visit 17	Day 1095 (Vac 1 +1094 days)	±30 days	FINAL VISIT: 12-month post-third study vaccination safety and immunogenicity visit

Table 15: Visit Windows: Expanded Safety Cohort (Cohort 3) - Two-dose Regimen and Month 12 Booster

VISIT	Visit Day	Window	Primary Purpose
Visit 1	Day 1	–	FIRST STUDY VACCINATION
Visit 2	Day 8	±2 days	7-day post-first study vaccination safety only visit
Visit 3	Day 15	±2 days	14-day post-first study vaccination safety and immunogenicity visit
Visit 4	Day 29	±3 days	28-day post-first study vaccination safety and immunogenicity visit
Visit 5	Day 57	±3 days	SECOND STUDY VACCINATION
Visit 6	Day 64 (Vac 2 +7 days)	±2 days	7-day post-second study vaccination safety only visit
Visit 7	Day 85 (Vac 2 +28 days)	-3/+10 days	28-day post-second study vaccination safety and immunogenicity visit
Visit 8	Day 183 (Vac 1 +26 weeks)	±14 days	26-week post-first study vaccination safety and immunogenicity visit
Visit 9	Day 365	–2 months	THIRD STUDY VACCINATION (MONTH 12 BOOSTER)
Visit 10	Day 372 (Vac 3 +7 days)	±2 days	7-day post-third study vaccination safety only visit
Visit 11	Day 393 (Vac 3 +28 days)	±3 days	28-day post-third study vaccination safety and immunogenicity visit
Visit 12	Day 547 (Vac 3 +26 weeks)	±14 days	26-week post-third study vaccination safety and immunogenicity visit
Visit 13	Day 730 (Vac 3 +12 months)	±1 month	FINAL VISIT: 12-month post-third study vaccination safety and immunogenicity visit

9.1.3. Screening Phase (Days -28 to 0 for Cohorts 1 and 2; Before Randomization on Day 1 for Cohort 3)

Only participants in good or stable health without acute illness or fever and complying with the inclusion and exclusion criteria as specified in Sections 4.1 and 4.2 will be included in the study. The investigator will provide detailed information on the study to the participants and will obtain written informed consent prior to each participant's participation in the study. All the procedures described in the [Schedule of Activities](#) will only take place after the written informed consent has been obtained.

The following evaluations will be performed to determine eligibility requirements as specified in the inclusion and exclusion criteria:

- Demographic information
- Medical history
- Review of pre-study medications

- Review of inclusion/exclusion criteria
- Full physical examination including vital signs measurement (respiratory rate, heart rate, supine systolic and diastolic blood pressure, and body temperature) and height and weight

The following evaluations will additionally be performed for participants in Cohorts 1 and 2:

- 12-lead ECG
- Serology testing (HIV type 1 or type 2, hepatitis B, hepatitis C)
- Blood sampling for laboratory safety testing (hematology and biochemistry)

Study participants who qualify for inclusion in Cohorts 1 and 2 will be contacted and scheduled for enrollment and first vaccination (Visit 2) within 28 days. If necessary, the screening visit may be split into several visits.

Participants in Cohorts 1 and 2 with laboratory values or vital signs (eg, elevated blood pressure) not meeting eligibility criteria at the screening visit may have 1 repeat testing at the discretion of the investigator if the abnormality is not clinically significant and may be a testing aberrancy. Enrollment of a participant with laboratory values representing toxicity Grade 2 is allowed if the investigator considers the values not to be clinically significant and reasonable for the population under study. Details on toxicity grade assessment are provided in Section 12.1.3.

After all data have been reviewed for completeness and adherence to the inclusion and exclusion criteria, the participant can be deemed eligible for the study.

SAEs (and any concomitant medications associated with SAEs) will be collected from first dose administration until the end of the study. Unsolicited AEs will be recorded on the Adverse Event page of the eCRF from the time of each vaccination through the following 28 days, together with information on any concomitant medications.^a Additionally, (S)AEs that are related to the study procedures or to non-investigational (concomitant) Janssen products will be collected from ICF signature onwards.

9.1.4. Randomization (Day 1)

Cohorts 1 and 2: After verification of selected inclusion and exclusion criteria,^b abbreviated physical examination (at the discretion of the investigator), and measurement of vital signs, eligible participants will be randomized as described in Section 5. If the medical status and/or physical examination suggest that significant changes have occurred since screening, the safety laboratory

^a AEs that start more than 28 days after a vaccination, but that are still present at the time of the next vaccination will also be recorded.

^b Inclusion criteria 4 and 5, and exclusion criteria 1, 4, 12, 13, and 14.

tests will be repeated and the randomization visit re-scheduled, or the participant excluded from the study if he or she fails to meet the inclusion and exclusion criteria.

Cohort 3: After verification of all inclusion and exclusion criteria, physical examination, and measurement of vital signs, eligible participants will be randomized as described in Section 5.

All eligible participants will receive their first vaccination following the procedures as described in Section 9.1.5.

9.1.5. Vaccination

On each vaccination day according to the schedules presented in Table 8, Table 9, Table 10 and Table 11, the following procedures will apply pre- and post-vaccination:

- Pre-vaccination, verification of selected inclusion/exclusion criteria,^a physical examination,^b and measurement of vital signs will be performed for all participants.
- Pre-vaccination, blood and nasal samples will be collected for immunogenicity assessments. In Cohorts 1 and 2, pre-dose blood samples will be taken on Day 1 for transcriptome analysis and safety laboratory tests (hematology and biochemistry).
- Pre-vaccination, the investigator must check for any symptoms of acute illness or fever (body temperature ≥ 38.0 °C). In such a situation, the participant may be vaccinated up to, and no later than 10 days after the scheduled vaccination, or withdrawn from further vaccination at the discretion of the investigator.
- Post-vaccination, participants will be closely observed for at least 30 minutes to monitor for development of any acute reactions, or longer if deemed necessary by the investigator. Vital signs measurement will be performed. Any unsolicited or solicited AEs and vital signs will be documented in the eCRF by study-site personnel following this observation period.
- All participants will be provided with a participant diary, thermometer, and ruler to measure and record body temperature, and solicited local and solicited systemic AEs for 7 days post-vaccination.
- Nasal swab kits and RTI Symptoms Forms will be distributed to all participants before the start of the first 2 RSV seasons of the study (relative to the enrollment date of the first participant in Cohort 1); during these RSV seasons, participants should record signs and symptoms of RTI using the RTI Symptoms Form.

^a To include receipt of any routine immunizations.

^b A full physical examination, including height and body weight, will be carried out at screening, and before final vaccination. At other vaccination visits, an abbreviated, symptom-directed examination will be performed if determined necessary by the investigator.

9.1.6. Post-Vaccination Follow-up

At 24 hours after vaccination on Day 1, a telephone call will be made to each sentinel participant in Cohort 1 to collect safety information (solicited and unsolicited AEs, SAEs, and concomitant medications).

The **7-day post-vaccination visits** include an abbreviated physical examination (at the discretion of the investigator), measurement of vital signs, and recording of any AEs/SAEs, concomitant medications and RTIs.^{a,b} The participant diary will be reviewed and collected. If the visit occurs before the end of the diary period after the vaccination, review of the diary will still take place, but the diary will be returned by the participant at the next study visit. In Cohorts 1 and 2, blood samples for transcriptome analysis and for safety laboratory tests (hematology and biochemistry) will be collected (after the first dose only, not applicable to subsequent doses).

The **14-day post-vaccination visit** (post-dose 1 and post-dose 3) includes an abbreviated physical examination (at the discretion of the investigator), measurement of vital signs, and recording of unsolicited AEs/SAEs, concomitant medications and RTIs.^a Blood and nasal samples for immunogenicity assessments will be collected. Blood samples for transcriptome analysis will also be taken (in Cohorts 1 and 2 only).

The **28-day post-vaccination visits** include an abbreviated physical examination (at the discretion of the investigator), measurement of vital signs, and recording of unsolicited AEs/SAEs, concomitant medications, and RTIs.^a Blood and nasal samples for immunogenicity assessments will be collected.

The **56-day post-vaccination visit** (post-dose 1 in Cohort 3 with one-dose regimen only) includes an abbreviated physical examination and vital signs measurement (both at the discretion of the investigator), and recording of any SAEs and concomitant medications, and RTIs.^a Blood and nasal samples for immunogenicity assessments will be collected.

The **12-week post-vaccination visit** (post-dose 1 in Cohort 3 with one-dose regimen only) includes an abbreviated physical examination and vital signs measurement (both at the discretion of the investigator), and recording of any SAEs and concomitant medications, and RTIs.^a Blood and nasal samples for immunogenicity assessments will be collected.

The **26-week post-vaccination visits** include an abbreviated physical examination and vital signs measurement (both at the discretion of the investigator) and recording of any SAEs and associated concomitant medications, and RTIs.^a Blood samples for immunogenicity assessments will be collected.

^a RTIs will only be recorded during the first 2 RSV seasons of the study (relative to the enrollment date of the first participant in Cohort 1).

^b Visit 13 (7 days post-third vaccination) is not required for any Cohort 3 participant who misses the third vaccination.

The **12-month post-first vaccination visit** includes an abbreviated physical examination and vital signs measurement (both at the discretion of the investigator) and recording of any SAEs and associated concomitant medications, and RTIs.^a Blood and nasal samples for immunogenicity assessments will be collected.

The **18-month post-first vaccination visit** (Cohort 2 only) includes an abbreviated physical examination and vital signs measurement (both at the discretion of the investigator) and recording of any SAEs and associated concomitant medications, and RTIs.^a Blood samples for immunogenicity assessments will be collected.

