Visit Day(s)	1	8 ^c	15	29	57	64 ^d	85 ^d	183	365	372 ^d	393 ^d	547 ^d	730 ^d	
Visit Window		±2 d	±2 d	±3 d	±3 d	±2 d	-3/+10 d	±14 d	-2 mo	±2 d	±3 d	±14 d	±1 mo	
Visit Type	Screening and STUDY VACCINATION 1	Safety	Safety and Immunogenicity	Safety and Immunogenicity	STUDY VACCINATION 2	Safety	Safety and Immunogenicity	Safety and Immunogenicity	STUDY VACCINATION 3	Safety	Safety and Immunogenicity	Safety and Immunogenicity	Safety and Immunogenicity	Early exit
Blood draw volumes:														
Participants with blood draws for both humoral and cellular responses (N=63)														
Approximate daily blood draw, mL	60	-	60	60	60	-	60	60	60	-	60	60	60	60
Approximate cumulative study blood draw, mL	60	60	120	180	240	240	300	360	420	420	480	540	600	-

AE: adverse event; d: day; ICF: informed consent form; mo: month; RSV: respiratory syncytial virus; RTI: respiratory tract infection; SAE: serious adverse event; vac: vaccination

① pre-dose; ② pre- and post-dose; ③ blood samples for immunogenicity will only be taken if the early exit is at least 14 days after the previous immunogenicity blood draw; ④ if within 7 days of the last vaccination; ⑤ if within 28 days of the last vaccination; ⑥ at the discretion of the investigator (based on health status of the participant)

Footnotes are presented on page 37.

Table footnotes for all cohorts:

- a. For those participants who are unable to continue participation in the study, but for whom consent is not withdrawn, an exit visit will be conducted as soon as possible.
- b. In addition, sentinel participants will be contacted by telephone 24 hours post-dose to collect safety information.
- c. If any of the participants for 7-day post-first study vaccine dose safety review come in earlier than Day 8 for Visit 3 in Cohorts 1 and 2, and Visit 2 in Cohort 3 (allowed window is ± 2 days), a subsequent phone call will be made at the end of the diary period to collect diary card information recorded between the actual visit and the end of the diary period on Day 8.
- d. The timings of the post-vaccination visits will be determined relative to the actual day of that vaccination.

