Injection site erythema is a redness of the skin caused by dilatation and congestion of the capillaries localized at the injection site. It can best be described by looking and measuring.

- **Injection Site Swelling/Induration**

Injection site swelling is a visible enlargement of an injected limb. It may be soft (typically) or firm (less typical). Injection site induration is a palpable thickening, firmness, or hardening of soft tissue, usually has well-demarcated palpable borders, can be visible (raised or sunken compared to surrounding skin), is often 'woody' to touch, and has a flat shape. As differentiation between swelling and induration may be difficult without a healthcare

^a AEs that start more than 28 days after a vaccination, but that are still present at the time of the next vaccination will also be recorded.

professional's assessment, both symptoms have been combined to allow self-assessment by the participants. Swelling and induration can best be described by looking and measuring.

Note: Any other injection site events not meeting the above case definitions should be reported separately as unsolicited AEs.^{22,23}

Systemic Adverse Events

Participants will be instructed on how to record daily body temperature using the thermometer provided for home use. Participants should record the temperature in the diary in the evening of each day of vaccination, and then daily for the next 7 days approximately at the same time each day.^a If more than 1 measurement is made on any given day, the highest temperature of that day will be used in the eCRF.

Fever is defined as an endogenous elevation of body temperature ≥ 38.0 °C, as recorded in at least one measurement.²⁶

In addition to fever, participants will be instructed on how to record daily in the diary for 7 days after each vaccination symptoms of the following events: fatigue, headache, myalgia, arthralgia, chills, and nausea. Severity of these event will be graded by the investigator according to the criteria presented in Section 12.1.3.

If a solicited local or solicited systemic AE is not resolved by 7 days after the vaccination, the follow-up will be captured on the diary. The participant will be instructed to record the date of last symptoms and maximum severity in the diary after resolution.

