ATTACHMENT 2: Transforming Solicited AE data into Analysis Format

Solicited AEs diary and onsite data in the SDTM FA and SR domains will both be remapped to the SDTM CE domain. They will be recorded by event in the CE domain, like the format of unsolicited AEs. The reported start date of an AE in the CE domain will be the date of first occurrence of the solicited AE. The last reported date will be used as the end date of the AE, regardless of possible changes in grade or time gaps, and taking into account if the AE continues after Day 8. The grade of the solicited AE (in CE) will be the maximum grade over the duration of the AE reporting period.

The derivation of the solicited AE ADAM dataset from SDTM CE will follow a similar approach to the derivation of the unsolicited AE ADAM dataset from SDTM AE. For observed solicited AE(s), one record per AE type will be derived per participant per post-dose period, pooling both onsite and diary records in the SDTM CE data. The start date of an AE will be derived as the first occurrence of that AE type (pooling the onsite and diary record) for a participant. The end date will be derived as the last end date between the onsite and diary record. The duration of a solicited AE will be recalculated in the ADAM dataset as: the derived end date – derived onset date + 1.

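### The diary is collected at the 7-day visit even when a solicited reaction is ongoing, although its end date and worst severity must later be written in that diary, so long durations may be under-recorded

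*Protocol*

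**What the plan says.** **Collection.** Protocol Section 9.1.6 states for the 7-day visits: "The participant diary will be reviewed and collected". If the visit falls before the diary period ends, the diary is still reviewed, "but the diary will be returned by the participant at the next study visit". No exception is made for a reaction that is still present.

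**Follow-up of unresolved reactions.** Section 9.2.3.1 says that if a solicited local or systemic AE "is not resolved by 7 days after the vaccination, the follow-up will be captured on the diary". It adds: "The participant will be instructed to record the date of last symptoms and maximum severity in the diary after resolution".

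**Timing.** Footnote c to the Schedule of Activities deals with early attendance after the first dose ("allowed window is ± 2 days"). In that case "a subsequent phone call will be made at the end of the diary period to collect diary card information", covering the days up to Day 8 only.

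**Later visits.** In the schedules, diary review appears only at the 7-day visits, and Section 17.4 places review there too. Section 9.1.1 moves the review to the next visit only if it was missed. For the 14-day and 28-day visits, Section 9.1.6 lists unsolicited AEs and SAEs and does not mention solicited reactions or the diary.

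**Analysis.** Protocol Section 11.5 and SAP Section 5.1.2 plan summaries of solicited AE duration, and the SAP counts it to resolution. SAP Attachment 2 says: "The last reported date will be used as the end date of the AE, regardless of possible changes in grade or time gaps". The same sentence adds that account is taken of continuation past Day 8. The grade is the highest over the reporting period.

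**The concern.** A participant cannot write the end of a reaction in a diary already handed in. A site that follows Section 9.1.6 literally takes away the document that Section 9.2.3.1 still needs, and it does so on the target day itself. A site that follows Section 9.2.3.1 leaves the diary out until the reaction ends. Whether a long reaction is fully recorded may then depend on the visit day and on which section the site follows.

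The output at stake is the solicited AE duration summary. The reactions affected are those lasting past the 7-day visit, so any shortfall falls on the upper end of the distribution and always in the same direction, towards shorter durations.

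**Working it through.** The plan gives no figure to reproduce. The check sets the sections side by side and counts days.

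**1. On which visit days do the instructions conflict?** The 7-day visit is Day 8 ± 2, so Days 6 to 10. Footnote c puts the end of the diary period on Day 8, and the Day 8 assessments may be made earlier that day to fit the clinic visit.

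| Visit day | Diary period still open? | Diary under 9.1.6 | Later entry under 9.2.3.1 possible? |
|---|---|---|---|
| 6, 7 | Yes | Kept until next visit | Yes |
| 8, 9, 10 | No | Collected | No |

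The conflict arises on 3 of the 5 permitted days. This counts calendar days, not participants.

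**2. Is there another stated route for the information?**
- The footnote c telephone call applies after the first dose only and stops at Day 8.
- The 14-day and 28-day visits name unsolicited AEs and SAEs only.
- The Synopsis and Section 3.1.2 require all AEs to be followed until resolution or stabilization. This covers solicited reactions, but no form or visit is named for recording their end.

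**3. What happens in the analysis?** Attachment 2 defines duration = end date − onset date + 1. Take an illustrative reaction with onset on Day 1, last diary entry on Day 8 and true resolution on Day 12:
- as recorded, if nothing is reported after collection: 8 − 1 + 1 = 8 days;
- true: 12 − 1 + 1 = 12 days;
- shortfall: 12 − 8 = 4 days.

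For Day 1 onset and collection on Day 8, 9 or 10, with reporting up to the visit, the longest diary-based duration is 8, 9 or 10 days.

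**4. Does the SAP handle an unrecorded end?** Attachment 2 gives no rule for showing a solicited AE as ongoing. The rule for a completely missing end date in SAP Section 5.1.3 belongs to the steps for unsolicited AEs. SAP Section 5.1.4 imputes nothing and limits the solicited analysis to documented data. If no resolution date was ever recorded, the last reported date stands in for one.

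**The case against.** The best defence is that this is a gap in wording, not a demonstrated loss of data. Section 9.2.3.1 is the specific instruction for unresolved reactions and could be read as overriding the general one. All AEs must be followed to resolution, Section 3.1.2 has sites confirm diary entries at subsequent visits, and the diary instructions and eCRF guidelines, which are not part of these documents, may supply the missing step. Safety is descriptive, duration is tabulated only for the most frequent events, and no decision rule uses it.

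Much of this stands, and it limits how far the point can be taken. A reader might infer any of the following, which the documents do not support:

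- **That end dates are lost.** Sites may obtain them through general AE follow-up, and Day 6 and Day 7 visits leave the diary in place. What is missing is a stated route.
- **That the SAP cuts reactions off at the diary's end.** Attachment 2 expressly allows for continuation beyond Day 8. Any shortening comes from collection, not from a SAP cut-off.
- **That the worst-grade tables are generally wrong.** Grades entered before collection are kept. Only a reaction that worsens afterwards would be under-graded.
- **That pausing rule 4 is weakened.** Section 11.9 requires same-day eCRF updating for Grade 3 or 4 AEs and notification within 24 hours for related AEs of Grade 3 or above. The 72-hour criterion does not wait on diary retrieval.

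What the defence does not answer is that Section 9.1.6 names one exception to collection and an ongoing reaction is not it.

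**Conclusion.** The contradiction is real and should be corrected. At visits on Days 8 to 10, Section 9.1.6 removes the diary that Section 9.2.3.1 still needs, and no later visit is assigned to retrieve the entry. The end date, and any rise in grade after collection, may go unrecorded. The SAP then relies on information whose recording the protocol can prevent.

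The consequence is confined mainly to the upper end of the duration summaries: 8 days in place of 12 in the illustration, which assumes that nothing is reported after collection. Incidence is little affected because the endpoint is defined over the 7 days after each vaccination. The median is little affected provided most reactions resolve before the visit.

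The number of reactions involved cannot be computed, because the documents give no rate of reactions ongoing at Day 8. The nearest figure is in Section 1.1: median durations of 1 to 3 days for the earlier Ad26.RSV.FA2 vaccine. That suggests a minority, but it concerns a different vaccine in adults aged 18 to 50, and turning it into a percentage would need a distribution that the documents do not supply.

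**What to change.** 1. **Protocol Sections 9.1.6 and 9.2.3.1.** Reconcile them: if a solicited AE is ongoing at the 7-day visit, the diary is reviewed and transcribed, but it (or a follow-up page) stays with the participant and is reviewed and collected at the next scheduled visit.
2. **Schedule of Activities.** Add that conditional review at the next visit, which is the 14-day visit where there is one and otherwise the 28-day visit.
3. **SAP Attachment 2.** Flag a solicited AE with no recorded resolution as ongoing, and show its duration as at least n days, not as ended at the last entry.

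The cost is wording in two protocol sections, one schedule entry and one SAP rule, using visits that already exist. For doses already given only the SAP change can still help, and it needs no new data collection.
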